9.2.2 Relationship to Study Drug

The Investigator's assessment of an AE's relationship to study treatment is part of the documentation process, but it is not a factor in determining what is or is not reported in the study. All AEs, regardless of relationship, will be recorded in the eCRF. In addition, SAEs will be reported to regulatory authorities as required by local regulation ([Section 9.3.4](#)).

The relationship or association of the study drug in causing or contributing to the AE will be characterized using the following classification and criteria presented in [Table 5](#).

Table 5 Guidelines for Determining the Relationship (if any) Between Adverse Event and the Study Drug

AE Relationship	Definition
Definite	This relationship suggests that a definite causal relationship exists between treatment administration and the AE, and that other conditions (concurrent illness, progression/expression of disease state, or concurrent medication reaction) do not appear to explain the event. The event reappears or worsens if the study treatment is re-administered.
Probable	This relationship suggests that a reasonable temporal sequence of the event with treatment administration exists and, based upon the known pharmacological action of the treatment, known or previously reported adverse reactions to the treatment or class of treatment, or judgment based on the Investigator’s clinical experience, the association of the event with the study treatment seems likely. The event disappears or decreases on cessation of study treatment.
Possible	This relationship suggests that the study treatment caused or contributed to the AE, i.e., the event follows a reasonable temporal sequence from the time of treatment administration or follows a known response pattern to the study treatment, but could also have been produced by other factors.
Unlikely Related	This relationship suggests an improbable (but not impossible) association between the study medication and the reported event.
Not Related	This relationship suggests no association between the study treatment and the reported event.

Abbreviation: AE = adverse event.

9.3 Serious Adverse Events

9.3.1 Serious Adverse Event Criteria

An SAE is defined as any event that results in death, is immediately life threatening, requires inpatient hospitalization or prolongation of existing hospitalization, results in persistent or significant disability/incapacity, or is a congenital anomaly/birth defect not present at Prescreening. Important medical events that may not result in death, be life threatening, or require hospitalization may be considered SAEs when, based upon appropriate medical judgment, they may jeopardize the patient or may require medical or surgical intervention to prevent one of the outcomes listed in this definition. Examples of such medical events include allergic bronchospasm requiring intensive treatment in an emergency room or at home, blood dyscrasias or convulsions that do not result in inpatient hospitalization, or the development of drug dependency or drug abuse. A life-threatening event does not include an AE that, had it occurred in a more severe form, might have caused death.

Serious AEs must be reported ([Section 9.3.4](#)) and will be followed through the follow-up visit. Serious AEs that occur after the final follow-up visit need not be reported unless the Investigator considers them related to study drug.

The Sponsor clinical physician will provide a Sponsor causality statement for all SAEs.

9.3.2 Suspected, Unexpected, Serious Adverse Reaction

A suspected, unexpected, serious adverse reaction (SUSAR) is an SAE for which there is a reasonable possibility that the drug caused the event, and this SAE has not been previously identified as an expected/listed adverse event. A list of expected AEs (if applicable) is provided in the current version of the IB and is considered the Reference Safety Information (RSI) for the study. Generally, the indication for which a product is intended would not be on the list of expected adverse events, but if it did occur, would not be considered “unexpected” for SUSAR reporting. As an example, a flare-up of neurological symptoms consistent with the underlying disease under treatment that required hospitalization would constitute an SAE; however, the event would not be considered unexpected. An exception would be if the reporter believed that investigational drug worsened the underlying neurological condition.

9.3.3 Serious Adverse Event Follow-up

Appropriate remedial measures should be taken by the Investigator using his/her best medical judgment to treat the SAE. These measures and the patient’s response to these measures should be recorded. All SAEs regardless of relationship to study drug will be followed by the Investigator until resolution. Clinical, laboratory, and diagnostic measures should be employed by the Investigator as needed to adequately determine the etiology of the event.

9.3.4 Serious Adverse Event Reporting

9.3.4.1 Reporting Requirements

Any AE that meets SAE criteria ([Section 9.3.1](#)) must be reported to the Sponsor and/or designee immediately (i.e., within 24 hours) after the time site personnel first learn about the event using the SAE Report Form provided for the study. Regardless of causality, all SAEs must be reported and will be collected and recorded from the time the patient signs the ICF until completion of the final follow-up visit. All SAEs must also be recorded in the patient’s source documentation and on the AE page of the patient’s eCRF.

The initial report should include at least the following information:

- Study Number
 - Patient’s identification number
 - Description of the event
 - Date and time of onset of the event
 - Seriousness criteria
 - Causality assessment to study drug
-

If follow-up is obtained, or requested by the Sponsor and/or designee, the additional information should be emailed on an SAE Report Form to the Sponsor and/or designee in a timely manner according to the procedures outlined above. Copies of discharge summaries, consultant reports, autopsy reports, and any other relevant documents may also be requested.

The Investigator will be responsible for reporting all SAEs to the Institutional Review Board (IRB) or Ethics Committee (EC). The Sponsor will be responsible for reporting to the regulatory authorities and Central Ethics Committees, as per local requirements.

9.4 Overdose

Study drug is to be administered by trained study staff. Administration will be performed in accordance with the IB and instructions in the Pharmacy Manual. Any incidence of overdose should be recorded as an SAE.

No clinical data are available regarding overdose with WVE-120101. As with any agent, if overdose occurs, general supportive measures and close observation should be instituted. Misuse of the study drug for illegal purposes is not expected in this study as patients have no direct access to the study drug.

9.5 Pregnancies

If a patient or the partner of a patient becomes pregnant during the course of the study, the pregnancy must be reported and monitoring of the mother and fetus should be conducted until the pregnancy outcome.

If a female patient becomes pregnant during the study, she must be discontinued from study drug; although the patient may continue to be followed in the study. The Medical Monitor should be notified by the Investigator and a Pregnancy Notification Form should be completed.

Any pregnancy (the patient or partner of a patient) should be followed until the outcome of the pregnancy is known.

Although pregnancy itself is not an SAE, serious complications of the pregnancy should be reported to the sponsor within 24 hours of knowledge by the Investigator (e.g., if the mother is hospitalized for dehydration) and an SAE form must be completed.

Based on the expected date of delivery, the Sponsor will attempt follow-up to determine the outcome of the pregnancy.

10 STATISTICAL CONSIDERATIONS

10.1 Sample Size Determination

No sample size calculations were performed. As this is an OLE, the maximum sample size is fixed by the number of patients completing the WVE-HDSNP1-001 study.

10.2 Disposition of Patients

Screened patients are defined as any patient who signed informed consent.

Enrolled patients consist of all screened patients who meet all eligibility criteria.

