9 ADVERSE EVENTS

The Investigator is responsible for reporting all AEs that are observed or reported during the study, regardless of their relationship to study treatment or their clinical significance.

Adverse event information will be collected beginning at enrollment (date of signed informed consent) and up to the end of the study. All ongoing AEs at the end of the study will be followed to resolution, or until the Investigator and the Sponsor agree that further follow-up is not required.

An AE is defined as any untoward medical occurrence in a patient enrolled into this study regardless of its causal relationship to study treatment. Patients will be instructed to contact the Investigator at any time after Screening if any symptoms develop.

A TEAE is defined as any event not present before exposure to study treatment or any event already present that worsens in either severity or frequency after exposure to study treatment.

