10.3 Analysis Populations

The safety population will include all enrolled patients who have received at least one dose of study medication in the OLE. The safety population will be the analysis set used for summaries of safety and clinical effects.

The per-protocol population will be a subset of the safety population and include patients with no major protocol deviations that will interfere with the assessment of the clinical effects' endpoints and with at least 80% compliance to the dosing regimen.

The PK population will consist of all patients in the safety population with at least one post-dose plasma or CSF concentration measurement.

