10.4.2 Analysis of Safety Data

The summary of safety results will be presented by dose group. All safety analyses will be performed on the safety population using the following common rules:

- The OLE baseline value is defined generally as the last available value from WVE-HDSNP1-001 before first dose in WVE-HDSNP1-002.
- The repeat dosing baseline value is defined generally as the last available value before initiation of repeat dosing. Initiation of repeat dosing can occur in either WVE-HDSNP1-001 or WVE-HDSNP1-002.
- Adverse event observation periods are defined as follows:
 - Pre-OLE treatment AEs are AEs that developed or worsened between the date of signed informed consent for the OLE and the date of first dose of study drug in the OLE.
 - OLE on-treatment adverse events are AEs that developed or worsened from the first dose of study drug in the OLE to study completion/discontinuation. Summaries of TEAEs will include all OLE on-treatment AEs.
 - Repeat dosing on-treatment adverse events are AEs that developed or worsened from the first dose of repeat dosing to study completion/discontinuation. Initiation of repeat dosing can occur in either WVE-HDSNP1-001 or WVE-HDSNP1-002. Summaries of repeat dosing TEAEs will include all repeat dosing on-treatment AEs.
- For quantitative safety parameters based on central laboratory/reading measurement descriptive statistics will be used to summarize results and change from baseline values by visit and dose group.

Adverse Events

Treatment-emergent AEs, treatment-emergent SAEs, and TEAEs leading to treatment discontinuation will be summarized by dose group based on Medical Dictionary for Regulatory Activities (MedDRA) coding of verbatim terms reported by investigators.

Adverse event incidence tables will present, by system organ class (SOC) and preferred term, the number and percentage of patients experiencing an AE. Multiple occurrences of the same event will be counted once in the tables. The denominator for computation of percentages is the safety population within each dose group.

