Adverse event incidence tables will present, by SOC and preferred term, the number and percentage of patients experiencing an AE by severity and by relationship to treatment. In tabulating the severity of adverse events, the highest severity will be assigned to a subject with more than one occurrence of the same adverse event. The highest level of association will be reported in subjects with differing relationships for the same adverse event.

Similar tables will be generated summarizing repeat dosing TEAEs. Listings of all AEs, SAEs, deaths, and AEs leading to study discontinuation will be provided.

Clinical Laboratory Evaluations

Summary statistics of laboratory variables including CSF safety laboratory variables will be calculated for each visit or study assessment by dose group. Laboratory data will also be categorized as low, normal, or high based on the reference ranges of the central laboratory. Frequencies and percentages will be presented by dose group for the shifts in these categories from baseline to post-baseline assessment time points. A listing of clinically significant hematology and chemistry findings will be provided.

Other Safety Evaluations

Summary statistics of vital signs, ECG, and height and weight variables will be calculated for each visit or study assessment by dose group.

Columbia-Suicide Severity Rating Scale

Listings of patients who respond “yes” to item 4 or 5 on the C-SSRS at any point in the study will be provided.

Immunogenicity

Anti-drug antibody assay results to WVE-120101 will be described categorically. Summary statistics for anti-drug antibody titer results will be provided.

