10.4.4 Clinical Effects and Pharmacodynamic Analyses

The change from baseline for clinical effects and PD endpoints will be summarized using a mixed model for repeated measures (MMRM) with the safety population. The MMRM will include the relevant baseline measure, time, dose-group and time by dose-group interactions. The MMRM will be used to construct 95% confidence intervals and to test if the change is statistically significant. Summaries will be based on data collected during the OLE and, separately, OLE data integrated with repeat dosing data from [WVE-HDSNP1-001](#).

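### Because Section 10.2 defines enrolled patients as those meeting every eligibility criterion, the safety population as written leaves out a dosed patient who proves ineligible

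*Combined protocol and SAP*

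**What the plan says.** Section 10.2 sets up two nested groups. First, "Screened patients are defined as any patient who signed informed consent". Second, "Enrolled patients consist of all screened patients who meet all eligibility criteria".

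Section 10.3 builds on the second group: "The safety population will include all enrolled patients who have received at least one dose of study medication in the OLE". The synopsis repeats this definition. Section 10.3 also makes the per-protocol and PK populations subsets of the safety population.

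Section 10.4.2 runs all safety analyses on the safety population and adds, for the adverse event tables, "The denominator for computation of percentages is the safety population within each dose group". Under Section 10.4.4 the clinical-effects and PD endpoints are "summarized using a mixed model for repeated measures (MMRM) with the safety population".

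Section 9 uses the same word in another sense: "Adverse event information will be collected beginning at enrollment (date of signed informed consent) and up to the end of the study".

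**The concern.** The primary objective is long-term safety and tolerability, so the safety tables should cover everyone exposed in the extension. As written, whether an exposed patient is counted depends on eligibility, and on which meaning of *enrolled* the programmer applies.

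The effect has no fixed direction. Leaving out an event-free patient raises an event rate; leaving out a patient with an event lowers it. Several exclusion criteria in Section 5.2 concern safety (liver enzymes, renal function, QTc, bleeding disorders, suicide risk), so the patients lost could be those at higher risk. That is plausible but not certain.

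The second meaning of enrolment also touches the adverse event definition itself. Section 9 says "An AE is defined as any untoward medical occurrence in a patient enrolled into this study regardless of its causal relationship to study treatment". Under the Section 10.2 meaning, an untoward event in a consented screen failure, or in a dosed ineligible patient, would not meet that definition, although collection starts at consent.

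**Working it through.** The plan states no figure to reproduce: Section 10.1 reports that no sample size calculation was done. The check is on the logic of the definitions, followed by an illustration of size.

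**Logic**

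1. Screened = signed consent (Section 10.2).
2. Enrolled = screened AND meets all criteria (Section 10.2).
3. Safety population = enrolled AND at least one dose in the extension (Section 10.3, synopsis).
4. Substituting: safety population = consented AND meets all criteria AND dosed. A dosed patient who fails any criterion is outside it, and therefore also outside the per-protocol and PK sets.

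**How enrolment is used elsewhere**

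- Section 4.1.1 places it after the screening tests, so it cannot be the consent date.
- Section 6.1 enrols patients who qualify, in line with Section 10.2.
- Section 9 equates it with the consent date, which Section 10.2 calls screened. Section 9 is the one that differs, and it does not settle which meaning Section 10.3 intends.

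**Can it happen?** Exclusion criterion 7a applies the ALT/AST limit at Baseline as well as at Screening. Section 8.1.7 sends safety samples, other than the local platelet and prothrombin test, to a central laboratory. A disqualifying Day 1 result could therefore arrive after the Day 1 dose. This is an inference, since no turnaround time is given.

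**Size (illustration)**

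Inputs: about 50 patients (Section 5). Two equal groups of 25 are an assumption, based on the optional 1:1 randomization in Section 4.1. The counts of ineligible patients and of events are also assumptions.

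Share of the exposed set lost per exclusion: 1/50 = 2.0% overall; 1/25 = 4.0% within a group.

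Table rate = events in eligible patients / (dosed − ineligible). All-dosed rate = (events in eligible patients + events in ineligible patients) / dosed. The range runs from no event to an event in every ineligible patient.

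| Dosed | Ineligible | Events in eligible patients | Rate as written | All-dosed rate, range |
|---|---|---|---|---|
| 50 | 1 | 0 | 0/49 = 0% | 0/50 = 0% to 1/50 = 2.0% |
| 50 | 1 | 2 | 2/49 = 4.1% | 2/50 = 4.0% to 3/50 = 6.0% |
| 50 | 2 | 2 | 2/48 = 4.2% | 2/50 = 4.0% to 4/50 = 8.0% |
| 25 | 1 | 1 | 1/24 = 4.2% | 1/25 = 4.0% to 2/25 = 8.0% |

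Exact (Clopper-Pearson) 95% intervals: 2/49, 0.5% to 14.0%; 3/50, 1.3% to 16.5%; 2/48, 0.5% to 14.3%; 4/50, 2.2% to 19.2%. They overlap widely.

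**The case against.** The best counter-argument is that meeting the criteria means being judged eligible at screening. Section 4.1.1 gives that decision to the investigator, Section 6.1 enrols those who qualify, and nothing revokes enrolment later; Section 5.3.1 deals with a significant deviation by withdrawal from the study. The structure of the populations points the same way. The per-protocol set removes certain major deviators from the safety set, so the safety set is presumably meant to contain them. Section 10.4.2 also starts the on-treatment period at the first dose, which suggests an exposure-based intent.

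This makes a wording slip more likely than a deliberate exclusion. It does not cure the text. Section 10.2 says nothing about a judgement made at screening, and the first-dose rule sits under the safety-population heading, so it cannot bring back a patient who is outside that population.

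It is also fair that the data are not lost. Events are collected under Section 9, reported if serious under Section 9.3.4, and probably listed, since Section 10.4.2 says "Listings of all AEs, SAEs, deaths, and AEs leading to study discontinuation will be provided" without naming a population. Patients also come from a completed parent study in which the investigator judged that they tolerated the drug, which may make ineligible dosing less likely. These points limit the harm to summary tables, denominators and models. They do not remove it.

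**Conclusion.** The concern holds. As written, the rule gives the wrong analysis set for the primary objective, because eligibility is a condition of entry to the safety population and no other text restores a dosed patient who fails it. Confidence is high for the literal reading; a milder reading is possible but is not what Section 10.2 states.

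The size depends on a number the documents do not give. Each dosed but ineligible patient removes about 2% of the exposed set, or 4% of a group if two groups of 25 are formed. In the illustrations, one or two such patients move a low event rate by up to about 4 percentage points (4.2% shown against 8.0%), in either direction and well within sampling error. The case for change is correct coverage of exposed patients, not a demonstrated large bias. It should be fixed.

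**What to change.** In Section 10.3 and the synopsis, define the safety population as all patients who received at least one dose of study medication in the extension, regardless of eligibility. Record eligibility violations as protocol deviations and let the existing major-deviation rule decide whether the patient stays in the per-protocol population.

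Use one meaning of enrolment. Sections 4.1.1, 6.1 and 10.2 already agree that it follows qualification, so the simplest course is to have Section 9 start collection at signed consent without calling that enrolment, and to word its adverse event definition for consented patients.

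The cost is one sentence in two places and a harmonised term in Sections 9 and 10.2. Data collection and study conduct do not change.

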10.3 Analysis Populations

The safety population will include all enrolled patients who have received at least one dose of study medication in the OLE. The safety population will be the analysis set used for summaries of safety and clinical effects.

The per-protocol population will be a subset of the safety population and include patients with no major protocol deviations that will interfere with the assessment of the clinical effects' endpoints and with at least 80% compliance to the dosing regimen.

The PK population will consist of all patients in the safety population with at least one post-dose plasma or CSF concentration measurement.

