5.1 Inclusion Criteria

1. Patient has documented ability to understand the written study ICFs and has provided signed written informed consent prior to any study procedures.
2. Patient successfully completed their Day 168 or 196 visit (depending upon dosing cohort and requirements in a given country) of the Phase 1b/2a study with WVE-120101, [WVE-HDSNP1-001](#).
3. In the opinion of the Investigator, the patient is able to tolerate all study procedures, is willing to comply with all other protocol requirements, and tolerated study drug in the parent study.
4. Patient is willing to practice highly effective contraception for the duration of the study if patients or their partners are of childbearing potential. Non-childbearing potential and highly effective methods of contraception are defined in the protocol ([Section 5.2.1](#)).

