10.4 Statistical Methods

Analysis will include summaries of data collected in this OLE study as well as integrated OLE data and repeat dosing data collected in WVE-HDSNP1-001.

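### The repeat-dosing TEAE tables can start counting in the parent study but include only patients later dosed in the OLE, so events that ended parent participation can be missed

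*Combined protocol and SAP*

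**What the plan says.** Four parts of the combined protocol and SAP bear on this.

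- **Window.** Section 10.4.2: "Repeat dosing on-treatment adverse events are AEs that developed or worsened from the first dose of repeat dosing to study completion/discontinuation". It adds that repeat dosing may begin in either study. Tables like the main AE tables are then promised for these events, with no other population named.
- **Analysis set.** Section 10.4.2 also states: "All safety analyses will be performed on the safety population using the following common rules". AE percentages use that population, within dose group, as denominator.
- **Who is in the set.** Section 10.3: "The safety population will include all enrolled patients who have received at least one dose of study medication in the OLE". Section 10.2 defines enrolment: "Enrolled patients consist of all screened patients who meet all eligibility criteria". Two criteria in Section 5.1 matter here. Inclusion 2 reads "Patient successfully completed their Day 168 or 196 visit". Inclusion 3 requires that the patient, in the investigator's opinion, "tolerated study drug in the parent study".
- **Integration.** Section 10.4 says that analyses will also summarise "integrated OLE data and repeat dosing data collected in WVE-HDSNP1-001", but Section 10.3 defines no population for that integrated material.

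**The concern.** In an extension study the patients are normally people who tolerated earlier treatment. That is an accepted limitation when the selection is finished before the observation window opens, as it is for the OLE-only tables. In the repeat-dosing tables it is not finished for everyone. For a patient whose repeat dosing began in WVE-HDSNP1-001, the window is already running when the patient is judged to have tolerated treatment and to be fit to continue. The parent part of the window is then counted only in those who passed.

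A patient whose parent repeat dosing ended in intolerance that prevented OLE entry appears in neither numerator nor denominator. A reader would naturally turn to this table for early repeat-dose tolerability, and these are the patients most informative about it. The outcomes at stake are TEAEs leading to discontinuation, intolerance, and serious or severe events that ended parent participation.

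**Working it through.** **Step 1. Reading the definitions together.** There is no planned figure to reproduce: Section 10.1 says that no sample size calculation was made, and about 50 patients is a planning number.

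| Patient | Repeat-dosing window opens | In safety population? | Parent repeat-dose events counted? |
|---|---|---|---|
| Repeat dosing begun in parent, then dosed in OLE | Parent study | Yes | Yes |
| Repeat dosing begun in parent, not dosed in OLE | Parent study | No | No |
| Repeat dosing begun in OLE | OLE | Yes | None to count |

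The second row is the problem. The third row is not affected by selection inside the window.

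**Step 2. Illustration for AE discontinuation.** The documents do not say how many parent patients were repeat-dosed or how many failed to enter the OLE. Apart from the 50, every input below is an assumption.

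- OLE patients: 50 (Section 5).
- m = number of the 50 who began repeat dosing in the parent study: 10, 25 or 50.
- d = share of parent repeat-dosed patients lost to the OLE for intolerance: 0% to 20%.
- q = AE-discontinuation rate seen in the 50: 5%, that is 50 × 0.05 = 2.5 patients.
- Each lost patient counts as one AE discontinuation.

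Lost patients = m × d / (1 − d). Rate in all repeat-dosed patients = (2.5 + lost) / (50 + lost).

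Worked case, m = 25 and d = 10%: lost = 25 × 0.10 / 0.90 = 2.78, and the rate is (2.5 + 2.78) / (50 + 2.78) = 10.0%.

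| m | Planned set | All, d = 0% | All, d = 5% | All, d = 10% | All, d = 20% |
|---|---|---|---|---|---|
| 10 | 5.0% | 5.0% | 6.0% | 7.1% | 9.5% |
| 25 | 5.0% | 5.0% | 7.4% | 10.0% | 15.6% |
| 50 | 5.0% | 5.0% | 9.8% | 14.5% | 24.0% |

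**Step 3. Check of direction for an AE unrelated to leaving.** Assume a constant hazard of 0.3 per year, 2.5 years of follow-up in patients who stay and 0.25 years in those who leave, with m = 50.

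- Stayers: 1 − exp(−0.3 × 2.5) = 52.8%.
- Leavers: 1 − exp(−0.3 × 0.25) = 7.2%.
- Planned set: 52.8%. With leavers added: 50.5% (d = 5%), 48.2% (d = 10%), 43.7% (d = 20%).

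Here crude incidence falls when the missing patients are added, only because they were watched for less time. The underlying rate is 0.3 per year in both groups. So the direction in Step 2 holds for events tied to leaving and not for AEs in general, and crude percentages alone would not be enough after the fix.

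**The case against.** The best defence is that Section 10.4 already promises the parent repeat-dosing data, so the omission is only apparent. But that sentence names no population, and the specific rule in Section 10.4.2 is not overridden. If Section 10.4 is read as bringing in every repeat-dosed parent patient, events would come from people outside the stated denominator. The two sections need reconciling on either reading.

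A second defence is that safety in these patients is covered elsewhere: the parent study is a randomised, placebo-controlled safety study, and the SMC reviews both datasets (Section 1.4). That is true, so this is not a gap in monitoring while the parent study runs. It does not repair a table that this plan produces separately, and SMC review of this study ends when the parent study is complete (Sections 4.4 and 13.1).

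Third, no loss has been shown. At the cutoffs in Section 1.4 no stopping criteria had been observed, and there were no related SAEs and no related TEAEs in the spinal cord and nerve root group. This stands as a limit on size. It does not establish that nobody was lost: the multiple-dose data then reached only 4 mg, and Section 1.4 does not report withdrawals or failures to enter the OLE.

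Several stronger readings are tempting and are not supported:

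- A reader might infer that the tables would show 0% for any event type that bars OLE entry. They would not, because the same type of event with onset in the OLE is counted and patients who start repeat dosing in the OLE are in the denominator.
- A reader might infer that every patient who stopped parent dosing for an AE is excluded. Inclusion 2 asks for a completed visit, not completed dosing, and Inclusion 3 is an opinion. Neither bars a patient merely for having had a severe or serious event.
- A reader might infer that the OLE-only TEAE tables share the fault. They do not; there the selection comes before the window.

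**Conclusion.** Wrong as written. The repeat-dosing TEAE rule can open the window in the parent study and then restricts numerator and denominator to patients selected, partly on tolerance, after it opened. Discontinuations, intolerance, and serious or severe events that ended parent participation are left out and can be understated.

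The size cannot be computed from the documents. It is zero if no repeat-dosed parent patient was lost for intolerance. Under the assumptions shown (m = 10 to 50, d = 5% to 20%, q = 5%), a planned-set figure of 5.0% corresponds to 6.0% to 24.0% among all repeat-dosed patients. This range illustrates the mechanism and is not an estimate. A reader might go further and conclude that repeat-dose harm is in fact understated, or that all AE rates are biased downward. The first needs a loss rate that the documents do not give, and Step 3 shows that the second need not be true.

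**What to change.** 1. In Section 10.3, add a repeat-dosing safety population: all patients who received repeat dosing of WVE-120101 in WVE-HDSNP1-001 or WVE-HDSNP1-002, whether or not they entered the OLE. Tie entry to the same first repeat dose that opens the window, so that a patient who stops soon after it is included.
2. In Section 10.4.2, use this population as both numerator source and denominator for the repeat-dosing TEAE tables, and give exposure-adjusted rates beside the crude percentages. The tables are by dose group, so say under which dose patients who never entered the OLE are shown.
3. Reconcile Section 10.4 with Section 10.4.2, so that the integrated data and the analysis set refer to the same patients.
4. In Section 10.2, report how many repeat-dosed parent patients did not enter the OLE and why (Day 168 or 196 visit not completed, tolerance criterion not met, other).
5. Keep the present safety population for the OLE-only tables. The mixed model in Section 10.4.4 is outside this point and need not change because of it.

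The cost is protocol and SAP wording and some programming, on parent-study data that the plan already intends to use. There is no new data collection and no patient burden. The repeat-dosing AE rates may look less favourable; if nobody was lost, they will not change.
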